**1.6. Summary of Clinical Experience**

TRK-250 has not previously been administered to humans.

**1.7. Study Rationale**

The principal aim of this study is to obtain safety and tolerability data when TRK-250 is administered by inhalation as single and multiple doses to subjects with IPF. A sequential-cohort, ascending-dose design has been chosen to optimize safety since Part A of the study will be the first time TRK-250 is administered to humans.

Conducting the study in subjects with IPF was considered necessary due to the paucity of data concerning administration of siRNA, in general, and TRK-250, specifically, to healthy subjects; a perception shared by regulatory authorities.

Inhaled administration has been chosen for the study since this is the intended route of clinical administration.

PK blood sampling is included in this trial design. This should advance understanding of the potential for inhaled TRK-250 to have off-target effects.

Once-weekly dosing frequency has been selected for Part B because 4 once-weekly intratracheal doses of TRK-250 were shown to be pharmacologically active in a human TGF- $\beta$ 1 [REDACTED] model.

Based on the nonclinical data, the duration of treatment in each part of this trial is considered adequate to achieve the study's objectives.

This study will be double blind and placebo controlled to avoid bias in the collection and evaluation of data. Placebo has been chosen as the control treatment to assess whether any observed effects are treatment related or simply reflect the study conditions.

Ongoing review of safety and tolerability data will be performed before deciding to proceed to the next dose escalation.

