### 3.1. Overall Study Design and Plan

#### 3.1.1. Part A

Part A will comprise a single-dose, single-period, sequential-cohort study. Potential subjects will be screened to assess their eligibility to enter the study within 28 days prior to study drug administration.

The total duration of study participation for each subject (from Screening through Additional Follow-up visit) is planned to be no more than 7 weeks but may be increased to a maximum

of 9 weeks if the Additional Follow-up visit is delayed based on findings from the ongoing review of data by the data monitoring committee (DMC).

It is planned that 16 subjects will be studied in 4 cohorts (Cohorts A1 to A4), each consisting of 4 subjects. Following DMC review of the safety and tolerability data from the first 4 cohorts, up to 3 further optional cohorts (Cohorts A5 to A7) of at least 4 subjects may be added to Part A to evaluate additional doses or to further evaluate planned doses.

[REDACTED]

[REDACTED]

All subjects will return for a Safety Follow-up visit 7 (+3) days after dosing and an Additional Follow-up visit 14 ( $\pm 3$ ) days after dosing. The timing of the Additional Follow-up visit for a cohort may be changed to a maximum of 28 ( $\pm 3$ ) days after dosing, based on emerging safety data.

In each of Cohorts A1 to A4, 3 subjects will receive TRK-250 and 1 subject will receive placebo. All doses will be administered in accordance with a randomization schedule on the morning of Day 1. Each subject will receive only a single dose of TRK-250 or placebo during the study. [REDACTED]

[REDACTED]

[figure not shown]
- Cohort A1: 2 mg
- Cohort A2: 10 mg
- Cohort A3: 30 mg
- Cohort A4: 60 mg

[REDACTED]

[REDACTED] pharmacologically active dose levels (ie, when the escalated dose will be  $\geq 34.7$  mg).

An overview of the study design and the planned dose levels are shown in [Figure 1](#).

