## 5. STUDY TREATMENTS

### 5.1. Description, Storage, Packaging, and Labeling

The IMP [REDACTED] will be supplied by the Sponsor (or designee), along with the batch/lot numbers and Certificates of Analysis. The IMP will be provided as a clear and sterile solution, formulated for inhalation via InnoSpire Go nebulizer system (Philips). [REDACTED]

The bulk drug container and unit dose containers will be labeled in accordance with national laws and regulations and packaged together with the diluent as kit boxes. Study treatment (IMP or placebo) will be prepared for administration by qualified site personnel in accordance with [Table 5](#).

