**7.2. Pharmacokinetic Assessments**

**7.2.1. Pharmacokinetic Sample Collection and Processing**

Blood samples for PK analysis will be collected by venipuncture or cannulation at the times indicated in the Schedule of Assessments in [Appendix 5](#). Changes to the scheduled times of PK assessments may be proposed based on emerging PK data. Final determination for revision of the PK schedule will be the responsibility of the Sponsor and the decision will be documented in the TMF.

Samples taken from subjects who received placebo will not be analyzed.

Procedures for collection, processing, and shipping of PK blood samples will be detailed in a separate document.

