- o Within 5 minutes after completion of dose administration and 10, 30, and 60 minutes after completion of dose administration, to assay for parent drug (TRK-250). PK sampling times are given as targets to be achieved within reasonable limits (eg, ±10%).

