10.3.2 Criteria for Handling Concentrations Below the Limit of Quantification in

Pharmacokinetic Analysis

- Concentration values that are below the limit of quantification (BLQ) will be set to zero, with defined exceptions as follows:
 - Any embedded BLQ value (between 2 quantifiable concentrations) and BLQ values following the last quantifiable concentration in a profile will be set to missing for the purposes of PK analysis.
 - If there are late positive concentration values following 2 BLQ concentration values in the apparent terminal phase, these values will be evaluated. If these values are considered to be anomalous, they will be set to missing.
 - If an entire concentration-time profile is BLQ, the profile will be excluded from the PK analysis.
 - If a predose concentration is missing, these values will be set to zero.

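### Placebo subjects give PK blood that is never assayed, so the visible plan has no bioanalytical check that the 4 (Part A) and 6 (Part B) pooled controls were unexposed

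*Protocol*

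**What the plan says.** Protocol 1.7 gives the purpose of the control arm: "Placebo has been chosen as the control treatment to assess whether any observed effects are treatment related or simply reflect the study conditions".

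Both schedules in Protocol Appendix 5 list PK blood sampling without exempting placebo subjects. There is a predose sample, followed by postdose samples: "Within 5 minutes after completion of dose administration and 10, 30, and 60 minutes after completion of dose administration". This applies on Day 1 in Part A and on Days 1 and 22 in Part B. Protocol 7.2.1 then states: "Samples taken from subjects who received placebo will not be analyzed". It gives no exception for a suspected error.

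On preparation, Protocol 5.1 says: "Study treatment (IMP or placebo) will be prepared for administration by qualified site personnel". Protocol 5.4 makes placebo visually indistinguishable from TRK-250.

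On numbers, Protocol 3.1.1 says: "In each of Cohorts A1 to A4, 3 subjects will receive TRK-250 and 1 subject will receive placebo". Protocol 3.1.2 gives each Part B cohort 4 active and 2 placebo subjects. SAP 7 pools placebo across the cohorts of each part.

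SAP 9 defines the Safety Population by receipt of at least one dose of either treatment. It does not say whether subjects are grouped by treatment received or treatment randomized. For active subjects, SAP 10.3.2 states: "If an entire concentration-time profile is BLQ, the profile will be excluded from the PK analysis".

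**The concern.** In a first-in-human safety study, the placebo group is the reference for judging whether a finding belongs to the drug. That reference is very small, so each control subject carries a lot of weight.

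The rule in 7.2.1 is partly circular. Samples are skipped because the subject is taken to have received placebo, but in the visible text the assay is the only measurement that could confirm this. Doses are prepared at multiple sites, and blinded staff could not see a preparation error when giving the dose. The other visible controls document what was dispensed and supervise how it was given. None measures what reached the subject.

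If a placebo subject were given TRK-250 and stayed in the placebo column, drug effects in that subject would count as background. The comparison at that dose would shift toward no difference.

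**Working it through.** **Planned counts.** There is no power calculation to reproduce, so the check starts from the planned counts.
- Part A: 4 cohorts × (3 + 1) = 16, as stated ("It is planned that 16 subjects will be studied in 4 cohorts (Cohorts A1 to A4), each consisting of 4 subjects"). Pooled placebo = 4 × 1 = 4.
- Part B: 3 cohorts × (4 + 2) = 18, as stated. Pooled placebo = 3 × 2 = 6.

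**One-way error: one placebo subject receives TRK-250.** Let μ1 be the expected outcome with drug, μ0 the expected outcome without it, and n the pooled placebo size. Assume that the subject is summarized as placebo and that the compared active group was dosed correctly and has the same effect level.
- Contaminated control mean = [(n − 1)μ0 + μ1]/n.
- Expected contrast = μ1 − [(n − 1)μ0 + μ1]/n = (μ1 − μ0)(n − 1)/n.
- Part A: contaminated share 1/4 = 25%; contrast retained 3/4 = 75%. Within that cohort, the only control is lost.
- Part B: contaminated share 1/6 = 16.7%; contrast retained 5/6 = 83%. This needs the error to cover all four weekly doses. One wrong dose out of four is a lesser exposure, and the formula does not describe it.

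**Illustration.** The adverse event rates are assumed, not taken from the documents: 10% on placebo and 50% on drug.
- The true difference of 40 points becomes 40 × 3/4 = 30 points in Part A, or 40 × 5/6 = 33.3 points in Part B.
- The chance of at least one event among the four Part A controls rises from 1 − 0.9^4 = 0.34 to 1 − 0.9^3 × 0.5 = 0.64.

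**Samples available from placebo subjects.** There are 1 predose + 4 postdose = 5 per PK day.
- All samples: 4 × 5 + 6 × 2 × 5 = 20 + 60 = 80.
- Postdose only: 4 × 4 + 6 × 2 × 4 = 16 + 48 = 64.
- One early postdose sample per PK day: 4 × 1 + 6 × 2 = 4 + 12 = 16.

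**Sensitivity of the check.** The documents give neither blood levels nor a lower limit of quantification. Let q be the chance that a single postdose sample from a dosed subject is quantifiable. One sample flags a misdosed subject with probability q. Four samples, if independent, do so with probability 1 − (1 − q)^4.

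| Assumed q (one sample) | Four samples |
|---|---|
| 0.05 | 0.19 |
| 0.10 | 0.34 |
| 0.20 | 0.59 |
| 0.50 | 0.94 |
| 0.90 | >0.99 |

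Samples from one subject are likely to be correlated, so the four-sample column is probably optimistic.

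**The case against.** The strongest reply is that the error is hypothetical and the plan is not blind to it. Drug is dispensed against a unique code from the interactive response system (5.3), dosing is supervised (5.5), disposition is recorded per subject and unused unit doses are kept (5.6), and a monitor verifies source data (Appendix 4). Table 5 and parts of 5.1 are redacted, so further preparation checks may exist. The sentence in 7.2.1 also turns on what was received. If accountability showed that a nominal placebo subject had been given TRK-250, that sentence would not bar the assay. All of this stands. It is why a reader should not infer that a mix-up could never be detected.

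A reader might also infer that neither side of a two-way swap would show. The SAP does not support that. Section 10.3.2 removes a profile that is entirely below quantification from the derivation of PK parameters, not from reporting. SAP 10.4 still lists concentrations, and SAP 10.4.1 counts such values as zeros in the summaries, so an active subject given placebo would remain visible. The signal is weak, because the SAP treats such profiles as foreseeable and states no query.

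A third tempting reading is a larger loss: 2/3 − 1/4 = 42% of the contrast retained in Part A and 3/4 − 1/6 = 58% in Part B. Those figures need a reciprocal swap that misdoses two subjects, sustained in Part B over all four doses. They do not describe one placebo subject receiving drug.

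Nor would harm be hidden. No inferential contrast is planned (Protocol 8.3, SAP 10.6.9), events are recorded whatever the arm, serious events go to pharmacovigilance within 24 hours, and the DMC reviews all available safety data before each escalation (Protocol 8.6). What could suffer is attribution to drug or background.

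**Conclusion.** The point holds as a modest improvement to Protocol 7.2.1. Blood is drawn from placebo subjects and left unassayed, and the visible plan contains no bioanalytical confirmation that the controls were unexposed. One undetected one-way error would contaminate 25% of the planned Part A pooled control and leave about 75% of the expected contrast. In Part B the figures are 16.7% and 83% if all four doses were affected.

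This rests on four assumptions: the error occurs, it is not caught by other means, the subject is summarized as placebo, and the drug has an effect at that dose. The documents give no evidence on how likely the error is, and no objective fails without the change. Optional cohorts would enlarge the pooled control and reduce the share.

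The proposed check has limits. A quantifiable placebo sample would be informative. A result below quantification would not prove correct dosing. Part B dosing errors on Days 8 and 15 fall outside the PK sampling days and would not be covered.

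**What to change.** **Protocol 7.2.1.** Replace the sentence on placebo samples with wording such as: *For each placebo subject, at least one early postdose sample per PK day (the one scheduled within 5 minutes of completing the dose) will be assayed to confirm treatment received. The remaining placebo samples will be assayed if TRK-250 is quantifiable or a dosing error is suspected.* If the sponsor's assay data suggest that one sample is too insensitive, the 64 postdose samples are already available.

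**Protocol 5.4.** State that, until unblinding, these results go only to unblinded bioanalytical staff or the DMC. The present text says only that interim bioanalytical data are provided in a blinded manner, and a report of a quantifiable placebo sample itself reveals an allocation. Any such sample should be queried through that restricted route.

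**SAP 9.** State that safety summaries group subjects by treatment actually received.

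Profiles entirely below quantification in active subjects should not be declared misallocations automatically. If blood levels are low, that rule would raise false alarms.

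**Cost.** About 16 extra sample assays on blood already collected, plus controlled release of the results. No extra visit, procedure or blood draw is needed.

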### 1.8. Benefit-Risk Assessment

Subjects with IPF in the current study are not expected to gain significant, long-term health benefits (beyond that of an assessment of their medical status) from participating in the study. The risks of participation are primarily those associated with adverse reactions to the investigational medicinal product (IMP), although there may also be some discomfort from collection of blood samples and other study procedures.

Although there is no evidence from nonclinical studies of bronchoconstriction following inhalation of TRK-250, subjects will have spirometry performed to assess for this important safety finding in this trial.

## 2. OBJECTIVES AND ENDPOINTS

### 2.1. Objectives

The primary objective of the study is to assess the safety and tolerability of single and multiple inhaled doses of TRK-250 in subjects with IPF.

The secondary objective of the study is to assess the PK in blood following single and multiple inhaled doses of TRK-250 in subjects with IPF.

### 2.2. Endpoints

#### 2.2.1. Primary Endpoints

The primary safety endpoints for this study are as follows:

- body weight
- vital signs measurements

- oxygen saturation (SpO2) by pulse oximetry
- hematology, clinical chemistry, and urinalysis test results
- 12-lead electrocardiogram (ECG) parameters
- forced expiratory volume over 1 second (FEV1), forced vital capacity (FVC)
- incidence and severity of adverse events (AE)

### 2.2.2. Secondary Endpoints

The single and multiple ascending dose PK outcome endpoints of TRK-250 are as follows (where applicable):

- AUC from time zero to the time of the last quantifiable concentration (AUC0-*t*last)
- Cmax
- Tmax

Other PK parameters may also be added.

[REDACTED]

[REDACTED]

[REDACTED]

[REDACTED]

[REDACTED]

[REDACTED]

[REDACTED]

[REDACTED]

[REDACTED]

## 3. INVESTIGATIONAL PLAN

This will be a double-blind, randomized, placebo-controlled study conducted in 2 parts, single and multiple inhaled dose, at multiple sites.

### 3.1. Overall Study Design and Plan

#### 3.1.1. Part A

Part A will comprise a single-dose, single-period, sequential-cohort study. Potential subjects will be screened to assess their eligibility to enter the study within 28 days prior to study drug administration.

The total duration of study participation for each subject (from Screening through Additional Follow-up visit) is planned to be no more than 7 weeks but may be increased to a maximum

of 9 weeks if the Additional Follow-up visit is delayed based on findings from the ongoing review of data by the data monitoring committee (DMC).

It is planned that 16 subjects will be studied in 4 cohorts (Cohorts A1 to A4), each consisting of 4 subjects. Following DMC review of the safety and tolerability data from the first 4 cohorts, up to 3 further optional cohorts (Cohorts A5 to A7) of at least 4 subjects may be added to Part A to evaluate additional doses or to further evaluate planned doses.

[REDACTED]

[REDACTED]

All subjects will return for a Safety Follow-up visit 7 (+3) days after dosing and an Additional Follow-up visit 14 ( $\pm 3$ ) days after dosing. The timing of the Additional Follow-up visit for a cohort may be changed to a maximum of 28 ( $\pm 3$ ) days after dosing, based on emerging safety data.

In each of Cohorts A1 to A4, 3 subjects will receive TRK-250 and 1 subject will receive placebo. All doses will be administered in accordance with a randomization schedule on the morning of Day 1. Each subject will receive only a single dose of TRK-250 or placebo during the study. [REDACTED]

[REDACTED]

[figure not shown]
- Cohort A1: 2 mg
- Cohort A2: 10 mg
- Cohort A3: 30 mg
- Cohort A4: 60 mg

[REDACTED]

[REDACTED] pharmacologically active dose levels (ie, when the escalated dose will be  $\geq 34.7$  mg).

An overview of the study design and the planned dose levels are shown in [Figure 1](#).

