**Figure 1: Study Schematic (Part A)**

**3.1.2. Part B**

Part B will comprise a multiple-dose, single-period, sequential-cohort study. Potential subjects will be screened to assess their eligibility to enter the study within 28 days prior to initial study drug administration.

The total duration of study participation for each subject (from Screening through Safety Follow-up visit) is planned to be no more than 10 weeks but may be increased to a maximum of 12 weeks if the Additional Follow-up visit is delayed based on findings from the ongoing review of data by the DMC.

[REDACTED]

[REDACTED]

[figure not shown]
All subjects will return for a Safety Follow-up visit approximately 7 days after their last dose (Day 29 [+3]) and an Additional Follow-up visit approximately 14 days after the last dose (Day 36 [ $\pm$ 3]). The timing of the Additional Follow-up visit for a cohort may be changed to a maximum of approximately 28 days after the last dose (Day 50 [ $\pm$ 3]), based on emerging safety data.

In each of Cohorts B1 to B3, 4 subjects will receive TRK-250 and 2 subjects will receive placebo. Doses will be administered on the morning of Days 1, 8, 15, and 22 in accordance with a randomization schedule. Each subject will receive 4 once-weekly doses of TRK-250 or placebo during the study. [REDACTED]

[REDACTED]

- Cohort B1: 10 mg
- Cohort B2: 30 mg
- Cohort B3: 60 mg

[REDACTED] shown in [Figure 2](#).

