## 7.1. Safety and Tolerability Assessments

### 7.1.1. Adverse Events

AE definitions, assignment of seriousness, severity, and causality, and procedures for reporting SAE are detailed in [Appendix 1](#).

The condition of each subject will be monitored from the time of signing the ICF to final discharge from the study. Subjects will be observed for any signs or symptoms and asked about their condition by open questioning, such as “How have you been feeling since you were last asked?”, at least once each day while resident at the study site and at each study visit. Subjects will also be encouraged to spontaneously report AE occurring at any other time during the study.

All nonserious AE, whether reported by the subject voluntarily or upon questioning, or noted on physical examination, will be recorded from initiation of study drug until study completion. SAE will be recorded from the time the subject signs the ICF until study completion. The nature, time of onset, duration, seriousness, and severity will be documented, together with an Investigator’s opinion of the relationship to study drug.

SAE will be followed up until the subject’s status reverts to baseline, the AE is determined by the Investigator to be irreversible, or death of the subject. Non-serious AE will be followed up until resolution or the AE is determined by the Investigator to be irreversible. This will be completed at the Investigator’s discretion. If not possible to follow up an SAE or AE, appropriate reasons should be provided.

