7 TREATMENTS

The following is a list of the masked study treatment abbreviations and ordering that will be used in the Closed Report.

Part A:

Cohorts	Treatment Order on TFLs
Cohort A1	TRK-250 2 mg
Cohort A2	TRK-250 10 mg
Cohort A3	TRK-250 30 mg
Cohort A4	TRK-250 60 mg
Cohort A...	... mg
All Cohorts in part A	Part A Pooled placebo

Up to 3 further optional cohorts (Cohorts A5 to A7) of at least 4 subjects may be added to Part A to evaluate additional doses or to further evaluate planned doses.

Part B:

Cohorts	Treatment Order on TFLs
Cohort B1	TRK-250 10 mg weekly
Cohort B2	TRK-250 30 mg weekly
Cohort B3	TRK-250 60 mg weekly
Cohort B...	... mg
All Cohorts in part B	Part B Pooled placebo

Up to 3 further optional cohorts (Cohorts B4 to B6) of at least 6 subjects may be added to Part B to evaluate additional doses or to further evaluate planned doses.

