10.6 Safety and Tolerability Assessments

10.6.1 Adverse Events

A pre-treatment adverse event (AE) is defined as an AE that starts after the subject has provided written informed consent and that resolves prior to the first dosing occasion, or an AE that starts prior to the first dosing occasion and does not increase in severity after dosing. A treatment-emergent AE (TEAE) is defined as an AE that occurs postdose or that is present predose and becomes more severe postdose.

All AEs will be listed. The TEAEs will be summarized by study part, treatment, severity, and relationship to the study drug. The frequency (the number of TEAEs, the number of subjects experiencing a TEAE, and the percentage of subjects experiencing a TEAE) of TEAEs will be summarized by treatment, and by Medical Dictionary for Regulatory Activities system organ class and preferred term. The summary and frequency TEAE tables will be presented for all causalities and for those TEAEs considered having reasonable possibility relationship to the study drug.

For any AEs that change severity ratings the AE will be included only once under the maximum severity rating in the summaries.

All study agent-related AEs, serious adverse events (SAE), AEs leading to withdrawal, AEs of severe intensity, life threatening and deaths will be listed separately.

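### If follow-up is extended for some cohorts only, the TEAE tables compare doses and pooled placebo over unequal observation time

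*Protocol*

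**What the plan says.** **Follow-up.** For Part A, protocol 3.1.1 plans: "All subjects will return for a Safety Follow-up visit 7 (+3) days after dosing and an Additional Follow-up visit 14" (±3) days after dosing. It then adds: "The timing of the Additional Follow-up visit for a cohort may be changed to a maximum of 28" (±3) days, on the basis of emerging safety data. For Part B, protocol 3.1.2 plans the last visit at Day 36 (±3), 14 days after the last dose on Day 22. Its timing for a cohort "may be changed to a maximum of approximately 28 days after the last dose (Day 50" ±3). In both parts the decision is made for a cohort, not for the whole part.

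**AE collection.** Under protocol 7.1.1, nonserious AEs "will be recorded from initiation of study drug until study completion". Both schedules in Appendix 5 mark AE recording at the Additional Follow-up visit, so collection lengthens when that visit moves.

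**Analysis.** SAP 10.6.1 states: "A treatment-emergent AE (TEAE) is defined as an AE that occurs postdose or that is present predose and becomes more severe postdose". No end date is attached. TEAEs are tabulated by treatment as number of events, number of subjects and percentage of subjects. SAP 7 gives one column per dose and one placebo column over all cohorts of the part ("Part A Pooled placebo", and the same for Part B). The readable text has no common cut-off, no person-time rate and no rule for unequal follow-up. SAP 12 declares no changes from the protocol's analyses.

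**The concern.** Incidence and severity of AEs is one of the primary safety endpoints (protocol 2.2.1), and protocol 3.4 says placebo is there to separate treatment effects from the conditions of the study. Length of observation is one of those conditions. If one dose is watched for longer than the other doses, and for longer than most of the pooled placebo subjects, its TEAE percentage rises with time alone.

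The extension is prompted by safety findings. The longer-observed cohort may therefore be one already under suspicion, and the artefact would then point the same way as the suspicion. At stake is how a descriptive dose trend, or an excess over placebo, is read in the study report.

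**Working it through.** **Inputs from the documents.** Part A: 3 active and 1 placebo per cohort, four cohorts, so 4 pooled placebo subjects. Part B: 4 active and 2 placebo per cohort, three cohorts, so 6 pooled placebo subjects. Observation from first dose is 14 or 28 days in Part A, and 36 − 1 = 35 or 50 − 1 = 49 days in Part B.

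**The plan's own durations reproduce.** Protocol 3.1.1 says Part A participation "is planned to be no more than 7 weeks but may be increased to a maximum" of 9 weeks. Screening + last visit + upper visit window gives 28 + 14 + 3 = 45 days (6.43 weeks), or 28 + 28 + 3 = 59 days (8.43 weeks) when extended. Part B: 28 + 36 + 3 = 67 days (9.57 weeks, stated limit 10) and 28 + 50 + 3 = 81 days (11.57 weeks, stated limit 12). The extension is thus built into the stated totals.

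**Ratio with no drug effect and a constant AE rate.** The expected ratio of TEAEs per subject equals the ratio of mean days observed. An extended cohort's own placebo subjects are extended with it.

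| Cohorts extended to the maximum | Mean pooled placebo days | Ratio to pooled placebo | Ratio to an unextended dose |
|---|---|---|---|
| Part A, one of four | (3×14 + 28)/4 = 17.5 | 28/17.5 = 1.60 | 28/14 = 2.00 |
| Part A, two of four | (2×14 + 2×28)/4 = 21 | 28/21 = 1.33 | 2.00 |
| Part A, three of four | (14 + 3×28)/4 = 24.5 | 28/24.5 = 1.14 | 2.00 |
| Part B, one of three | (4×35 + 2×49)/6 = 39.7 | 49/39.7 = 1.24 | 49/35 = 1.40 |

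**Early clustering (Part A, one cohort extended).** Set the events in 14 days to 1. Let a share f fall in the first 7 days, with the rate of the second week continuing to Day 28. Events by Day 28 are then E = 1 + 2(1 − f), and the ratio to pooled placebo is E/[(E + 3)/4].
- f = 0.50: E = 2.0, ratio 1.60.
- f = 0.75: E = 1.5, ratio 1.33.
- f = 0.90: E = 1.2, ratio 1.14.

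If f = 0.90 and three cohorts are extended, the ratio is 1.2/[(3×1.2 + 1)/4] = 1.04.

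**Percentage of subjects.** The documents give no background AE rate, so I assume 20%, 40% or 60% of subjects have a TEAE by the planned last visit, with a constant rate and one cohort extended.
- Part A: P(28 days) = 1 − (1 − p)² = 36%, 64%, 84%. Pooled placebo = (3p + P)/4 = 24%, 46%, 66%. Excess 12, 18, 18 points.
- Part A with three cohorts extended: pooled placebo = (p + 3P)/4 = 32%, 58%, 78%. Excess 4, 6, 6 points.
- Part B: P(49 days) = 1 − (1 − p)^1.4 = 26.8%, 51.1%, 72.3%. Pooled placebo = (4p + 2P)/6 = 22.3%, 43.7%, 64.1%. Excess about 5 to 8 points.

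With 3 active subjects, 12 to 18 points is 0.36 to 0.54 of one subject.

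**The case against.** The strongest reply is that this is contingent and small. The protocol permits the extension but does not plan it. The data monitoring committee reviews safety between escalations (protocol 8.6), so a finding could as easily lengthen follow-up for several later cohorts, which shrinks the contrast with placebo. Many AEs after a single inhaled dose may come early. One subject moves a three-subject column by 33 points, more than the artefact itself. All AEs are listed and onset times are collected, so late events can be identified individually. The table shells are not public and some protocol text is redacted, so a window rule there cannot be excluded. All of this stands, and it limits the weight of the point. It does not supply a rule in the SAP's AE section.

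A reader might infer more than the documents support:
- *That an extended dose will show more AEs.* This needs the option to be used, for some cohorts only, with AEs still accruing late. With so few subjects, realised counts may not show it.
- *That follow-up doubles in both parts.* It does in Part A. In Part B only the time after the last dose doubles.
- *That the contrast is 2.8-fold*, from 31 against 11 days. That sets opposite ends of two visit windows against each other and is not an expected difference.
- *That progressive disease will drive the excess.* Entry requires a life expectancy of at least 12 months and excludes recent exacerbation or respiratory infection. No rate of disease-related events is given.
- *That escalation decisions are biased.* Protocol 8.6 bases them on all available safety data, not on the final TEAE percentages.

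**Conclusion.** The point holds conditionally. If some cohorts are extended and others are not, the TEAE tables as specified compare columns with unequal observation time on a primary safety endpoint.

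In Part A, an extended dose has twice the observation time of an unextended one. Against pooled placebo, the expected no-effect ratio of TEAEs per subject is about 1.1 to 1.6 when either the number of extended cohorts or the early clustering of AEs is varied. It comes nearer to 1 if several cohorts are extended and AEs also cluster strongly. In Part B the factor is 1.4 against an unextended dose and about 1.24 against pooled placebo with one cohort extended. These figures assume extension to the permitted maximum and no drug effect. The percentage-point figures rest in addition on assumed background rates.

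No test is affected, because safety analysis is descriptive. The comparison of active with placebo inside an extended cohort is not distorted, because both arms are extended. This is a worthwhile low-cost improvement to the SAP, not a flaw in the design.

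**What to change.** In SAP 10.6.1, before database lock:
- Keep the all-TEAE tables as planned.
- Add TEAE incidence tables by dose and pooled placebo over one window common to all cohorts of a part, counting onset up to the originally planned Additional Follow-up: 14 days after dosing in Part A, 14 days after the last dose in Part B.
- State that the common-window tables are the ones used for dose-to-dose and dose-to-placebo comparison.
- Show subject-days of follow-up for each column.
- Tabulate TEAEs with later onset separately.

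Apart from visit-window differences, this returns the expected no-effect ratio to 1.00. The cost is one extra set of AE tables, and no new data are needed because onset time is already recorded. Small differences remain from the ±3-day window: a subject last seen on Day 11 is observed for less than the full window, and events on Days 15 to 17 in unextended Part A cohorts fall in the later-onset table. The subject-days make this visible. Keeping the all-TEAE tables means that no late event drops out of the overall incidence of a first-in-human study. The extension rule, the visits and the clinical decisions are unchanged.
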